**Table 11. Approximate Blood Volume Collection for Cohorts 3 (210 mg SC), 4 (420 mg SC), and 5 (700 mg SC)**

Test	Volume per Collection, mL	Number of Collections	Total Volume, mL
Clinical chemistry	8.5	13	110.5
Clinical hematology	4	7	28
Coagulation labs	2.7	8	21.6
Screening lipid panel*	8.5	1	N/A
On-study lipid panel	9	7	63
Pregnancy test (females only)*	8.5	1	N/A
HIV, HBsAg, HBcAb, HepCAb	8.5	1	8.5
Serum FSH (females only)*	8.5	1	N/A
Blood for biomarker development	14.5	4	58
Alkaline phosphatase isoenzyme	5	4	20
Pharmacogenetics (optional)**	3	1	N/A
AMG 529 PK serum concentration	5	15	75
Anti-AMG 529 Antibody	5	2	10
TOTAL			394.6

\* Collected in the same tube as Clinical chemistry lab

\*\* Obtained from cell pellet from the biomarker plasma sample collection at pre-dose (day 1) only

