## 3. EXPERIMENTAL PLAN

### 3.1 Study Design

This is a phase 1, randomized, double-blind, placebo-controlled, ascending single-dose study in healthy subjects.

Approximately 48 subjects will enroll in 1 of 6 dose cohorts (8 per cohort). For cohorts 1, 2, 3, 4, and 5, eight (8) subjects will be randomized to receive AMG 529 or placebo SC in a 3:1 ratio at dose levels of 21, 70, 210, 420, and 700 mg, respectively.

In cohort 6, eight (8) subjects will receive AMG 529 or placebo IV in a 3:1 ratio at a dose level of 70 mg.

For all cohorts, the first 2 subjects (sentinel pair) will be randomized such that 1 subject will receive AMG 529 and 1 subject will receive placebo, and observed for at least 24 hours before the remaining subjects in the cohort are dosed, provided there are no safety or tolerability concerns as assessed by the principal investigator.

Escalation to a higher dose cohort will only proceed when the previous dose regimen has been found to be safe and reasonably tolerated based on available safety and laboratory data through study day 15 for all subjects and upon unanimous decision at the Dose Level Review Meeting (DLRM). Enrollment can be initiated in cohort 5 and cohort 6 after the dose regimen in cohort 4 has been found to be safe and well tolerated. Cohort 6 will start enrollment after the completion of cohort 5 enrollment.

The overall study design is described by a [study schema](#) at the end of the protocol synopsis section.

The study endpoints are defined in [Section 10.1.1](#).

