**Table 5. Schedule of Assessments for Cohorts 3, 4, and 5**

Activity	Screening		Treatment																EOS
	Study Day		1				2		3	4	6	8	11	15	22	30	43	57	
Time (in hours) a			Pre-Dose	0	6	12	24	36	48	72	120	168	240	336	504	696	1008	1344	
Informed Consent	X																		
In-House Residency		X <	> X																
Medical History	X	X																	
Body Weight	X																		X
Body Mass Index	X																		
Height	X																		
Vital Signs (HR, RR, BP, TEMP)	X	X	X		X	X	X		X	X	X	X	X	X	X	X	X	X	X
Physical Examination	X	X																	X
12-lead ECG b	X		X		X	X	X		X	X	X	X	X	X	X	X	X	X	X
eGFR	X	X																	X
Clinical Chemistry c	X	X					X		X d	X	X d	X d	X	X d	X	X	X d	X	X
Clinical Hematology	X	X					X			X						X	X		X
PT/INR and aPTT	X	X					X			X					X	X	X		X
Urinalysis	X	X					X			X				X		X	X		X
Screening Lipid Panel c	X																		
On-study Lipid Panel c			X						X		X		X		X	X			X
Drug and Alcohol Screen	X	X																	
HIV, HBsAg, HBcAb, HepCAb e	X																		
Pregnancy Test (females only)	X	X																	X
Serum FSH Test (females only) f	X																		
Randomization		X																	
Study Drug Administration				X															
Anti-Drug Antibody Sample Collection			X																X
PK Sample Collection			X g		X	X	X	X	X	X	X	X	X	X	X	X	X	X	X
Alkaline phosphatase isoenzymes			X						X			X					X		
Collect blood for biomarker development h			X						X			X					X		
Pharmacogenetic (optional) i			X																
Adverse Event Recording				X <	> X														
Serious Adverse Event Recording	X <																		> X
Concomitant Medications	X <																		> X

a Time in hours are relative to IP administration

b A single ECG will be collected at screening. Prior to dosing day 1, 3 baseline ECGs will be collected approximately 30 minutes apart. Each baseline ECG will be in triplicate to be collected 30 seconds apart for a total of 9 ECGs. Triplicate ECGs, to be collected 30 seconds apart, will be collected at all timepoints after dosing on day 1.

c 10 hour fasting is required at all time points

d Alkaline phosphatase only on days 3, 6, 8, 15, and 43

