**Table 10. Approximate Blood Volume Collection for Cohorts 1 (21 mg SC) and 2 (70 mg SC)**

Test	Volume per Collection, mL	Number of Collections	Total Volume, mL
Clinical chemistry	8.5	11	93.5
Clinical hematology	4	6	24
Coagulation labs	2.7	7	18.9
Screening lipid panel*	8.5	1	N/A
On-study lipid panel	9	6	54
Pregnancy test (females only)*	8.5	1	N/A
HIV, HBsAg, HBcAb, HepCAb	8.5	1	8.5
Serum FSH (females only)*	8.5	1	N/A
Blood for biomarker development	14.5	4	58
Alkaline phosphatase isoenzyme	5	4	20
Pharmacogenetics (optional)**	3	1	N/A
AMG 529 PK serum concentration	5	13	65
Anti-AMG 529 Antibody	5	2	10
TOTAL			351.9

\* Collected in the same tube as Clinical chemistry lab

\*\* Obtained from cell pellet from the biomarker plasma sample collection at pre-dose (day 1) only

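### As the text reads, the 210, 420 and 700 mg cohorts have no scheduled blood count between day 4 and day 22, so the day-15 reviews after 210 and 420 mg have none from that cohort later than day 4

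*Protocol*

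**What the plan says.** **Schedules.** Protocol Section 7.1 has two schedules of assessments. Table 4 covers cohorts 1, 2 and 6 (21 mg SC, 70 mg SC, 70 mg IV). It puts hematology, coagulation and urinalysis on the same seven occasions: screening and days -1, 2, 4, 11, 22 and 30. Table 5 covers cohorts 3, 4 and 5 (210, 420, 700 mg SC). Leaving out empty cells, its rows read "Clinical Hematology X X X X X X X", "PT/INR and aPTT X X X X X X X X" and "Urinalysis X X X X X X X X".

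**Volumes.** Section 7.6 gives draw counts. For cohorts 3 to 5, Table 11 has "Clinical hematology 4 7 28" and "Coagulation labs 2.7 8 21.6". For cohorts 1 and 2, Table 10 has "Clinical hematology 4 6 24". Table 12 (cohort 6) has the same hematology count as Table 10.

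**Escalation.** Under Section 3.1 a higher dose opens only when the previous one is judged safe "based on available safety and laboratory data through study day 15 for all subjects". Safety laboratory analytes are part of the primary endpoint (Section 10.1.1.1). Protocol Section 10.5.2.1.4 and SAP Section 9.6.3 summarize them by visit and cohort.

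**The concern.** The larger doses appear to have the thinner hematology monitoring, and the protocol gives no reason. A lower-dose SC cohort reaches its day-15 review with scheduled counts from days 2, 4 and 11. The 210 and 420 mg cohorts reach theirs with days 2 and 4 only. Those two reviews decide the steps to 420 and 700 mg, and the review after 420 mg also allows the IV cohort to open.

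The protocol anticipates a half-life of 7 to 10 days (Section 2.5), so a delayed effect on red cells, white cells or platelets could fall wholly inside the gap. The amendment added mean platelet volume to the panel, so the sponsor has some interest in these parameters. In the final tables, the day-11 hematology summary would have no 210, 420 or 700 mg group, and no dose trend could be read at that visit.

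**Working it through.** **1. Marks per row, against the volume tables**

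| Row | Table 4 marks | Tables 10 and 12 | Table 5 marks | Table 11 |
|---|---|---|---|---|
| Hematology | 7 | 6 | 7 | 7 |
| Coagulation | 7 | 7 | 8 | 8 |
| Urinalysis | 7 | no blood | 8 | no blood |

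**2. Where the Table 5 hematology marks fall**

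The header has 18 columns: screening, day -1, pre-dose, and 0, 6, 12, 24, 36, 48, 72, 120, 168, 240, 336, 504, 696, 1008 and 1344 h. The extracted hematology row has 19 cells. The surplus is 19 − 18 = 1, so on this text a mark can sit at most one column too far right.

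- The first four marks are at screening, day -1, 24 h (day 2) and 72 h (day 4).
- The fifth mark is in cell 16. With no shift that is 696 h (day 30). With a one-column shift it is 504 h (day 22). A mark at day 15 or earlier would need a shift of two or more.
- The last mark lies one cell past the header and can only be the end-of-study visit (day 57). The one-column reading of the late block is therefore days 22, 30 and 57.
- The footnotes do not fix one alignment for every row. The biomarker footnote (last sample day 30) implies a one-column shift, while the footnote on ALP-only chemistry days (including day 43) implies none in the chemistry row.
- The same test applied to the other panels puts the first coagulation mark after day 4 at day 15 or 22, and the first urinalysis mark at day 11 or 15.

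On either alignment, hematology has no mark after day 4 and before day 22.

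**3. Length of the gap**

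- Cohorts 3 to 5: 22 − 4 = 18 days, or 30 − 4 = 26 days with no shift.
- Cohorts 1, 2 and 6: 11 − 4 = 7 days, then 22 − 11 = 11 days.
- In anticipated half-lives after dosing, the day-4 draw (72 h, 3 days) is at 3/10 = 0.3 to 3/7 = 0.4. A day-11 draw (240 h, 10 days) is at 10/10 = 1.0 to 10/7 = 1.4. The day-22 draw (504 h, 21 days) is at 21/10 = 2.1 to 21/7 = 3.0.

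**4. Subjects affected**

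- 3 cohorts × 8 = 24 of 48 subjects, of whom 3 × 6 = 18 of 36 receive AMG 529.
- Pooled placebo with day-11 hematology: 3 × 2 = 6, against 6 × 2 = 12 if all cohorts had the draw.

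**5. Volumes**

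- Table 11 as printed: 110.5 + 28 + 21.6 + 63 + 8.5 + 58 + 20 + 75 + 10 = 394.6 mL, which reproduces the stated total. With 8 hematology draws, 8 × 4 = 32 mL and the total is 398.6 mL.
- Tables 10 and 12 as printed sum to 351.9 and 361.9 mL, as stated. With the 7 draws of Table 4, 7 × 4 = 28 mL and the totals are 355.9 and 365.9 mL.

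**The case against.** **The table text is damaged.** The Table 5 chemistry row shows 14 marks where Table 11 counts 13, and the PK row shows 16 where Table 11 counts 15. The footnotes give conflicting anchors, so exact late days cannot be trusted. This stands, and it is why confidence is moderate. It does not remove the gap, because a one-cell surplus cannot move a mark from day 22 to day 11. The copy of Table 5 in the amendment's change description prints hematology and coagulation alike, but with ten marks each. It matches no other table and is not the current text.

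**Table 11 is weak confirmation.** All three volume tables put hematology one below coagulation, although Table 4 schedules the two equally. If Section 7.6 undercounts hematology throughout, the true figure for cohorts 3 to 5 is 8. This also stands. Table 11 supports the Table 5 count but does not prove it, and it gives no days.

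**The consequence is softened elsewhere.** Section 7.2.5.14 allows additional safety tests if clinically indicated. Section 6.2.1.2.1 has earlier cohorts' data considered and lets the review delay dosing. An unblinded medical monitor reviews data continuously and may suspend dosing. A subject dosed about a week before the last one in the cohort could already have a day-22 count. A reader might infer that the reviews can see no blood count after day 4 at all. The documents do not support that. The point is limited to scheduled counts from the cohort under review.

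**Fewer hematology draws may be deliberate.** The toxicology summary (Section 2.2.3) reports changes in ALP, GGT and prothrombin time and no blood-count finding, so one more coagulation than hematology draw is defensible. Nor can a reader infer that the other panels are all drawn on day 11 at these doses: coagulation reads as day 15 or 22. The case for day 11 rests on Table 4, not on parity within Table 5.

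**Conclusion.** The point holds for scheduled draws, with moderate confidence. On the current text, cohorts 3 to 5 have post-dose hematology on days 2 and 4 and then none until day 22 or later, while cohorts 1, 2 and 6 have a day-11 count. The two escalation reviews affected are those after 210 and 420 mg. At 700 mg no further SC escalation is planned, so the loss there is to the safety summary.

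The conclusion assumes that the extracted Table 5 row has lost no mark and is displaced by no more than its one surplus cell. It does not show that the reviews would be unsafe or that a blood-count effect is expected. It is worth acting on because the remedy is small and serves part of the primary endpoint. The 4 mL discrepancies in Tables 10 and 12, which are titled as approximate, are editorial.

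**What to change.** 1. Check the Clinical Hematology row of Table 5 in the source document.
2. If the gap is confirmed, add Clinical Hematology at day 11 (240 h) for cohorts 3 to 5, matching Table 4, and change Table 11 to 8 collections, 32 mL, total 398.6 mL. With the ±1 day visit window the sample is taken by day 12, before the day-15 cut.
3. If the source Table 5 already has the day-11 draw, correct Table 11 alone, to the same figures.
4. In either case, reconcile the hematology counts in Tables 10 and 12 with Table 4. If Table 4 governs, they become 7 collections and 28 mL, with totals of 355.9 and 365.9 mL.

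The cost of step 2 is one 4 mL tube in each of 24 subjects and a short amendment. Day 11 is already a visit with chemistry and PK blood draws, and hematology is analyzed locally, so no visit is added.

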**Table 12. Approximate Blood Volume Collection for Cohort 6 (70 mg IV)**

Test	Volume per Collection, mL	Number of Collections	Total Volume, mL
Clinical chemistry	8.5	11	93.5
Clinical hematology	4	6	24
Coagulation labs	2.7	7	18.9
Screening lipid panel*	8.5	1	N/A
On-study lipid panel	9	6	54
Pregnancy test (females only)*	8.5	1	N/A
HIV, HBsAg, HBcAb, HepCAb	8.5	1	8.5
Serum FSH (females only)*	8.5	1	N/A
Blood for biomarker development	14.5	4	58
Alkaline phosphatase isoenzyme	5	4	20
Pharmacogenetics (optional)**	3	1	N/A
AMG 529 PK serum concentration	5	15	75
Anti-AMG 529 Antibody	5	2	10
TOTAL			361.9

\* Collected in the same tube as Clinical chemistry lab

\*\* Obtained from cell pellet from the biomarker plasma sample collection at pre-dose (day 1) only

## 7.7 Sample Storage and Destruction

Any blood, biomarker, and PK samples collected according to the Schedule of Assessments ([Table 4](#) and [Table 5](#)) can be analyzed for any of the tests outlined in the protocol and for any tests necessary to minimize risks to study subjects. This includes testing to ensure analytical methods produce reliable and valid data throughout the course of the study. This can also include, but is not limited to, investigation of unexpected results, incurred sample reanalysis, and analyses for method transfer and comparability.

All samples and associated results will be coded prior to being shipped from the site for analysis or storage. Samples will be tracked using a unique identifier that is assigned to the samples for the study. Results are stored in a secure database to ensure confidentiality.

If informed consent is provided by the subject, Amgen can do additional testing on remaining samples (ie, residual and back-up) to investigate and better understand cardiovascular diseases, the dose response and/or prediction of response to AMG 529, characterize antibody response, and characterize aspects of the molecule

(eg, mechanism of action/target, metabolites). Results from this analysis are to be documented and maintained, but are not necessarily reported as part of this study. Samples can be retained for up to 20 years.

Since the evaluations are not expected to benefit the subject directly or to alter the treatment course, the results of pharmacogenetic, biomarker development, or other exploratory studies are not placed in the subject's medical record and are not to be made available to the subject, members of the family, the personal physician, or other third parties, except as specified in the informed consent.

The subject retains the right to request that the sample material be destroyed by contacting the investigator. Following the request from the subject, the Investigator is to provide the sponsor with the required study and subject number so that any remaining blood samples and any other components from the cells can be located and destroyed. Samples will be destroyed once all protocol-defined procedures are completed. However, information collected from samples prior to the request for destruction, will be retained by Amgen.

The sponsor is the exclusive owner of any data, discoveries, or derivative materials from the sample materials and is responsible for the destruction of the sample(s) at the request of the subject through the investigator, at the end of the storage period, or as appropriate (eg, the scientific rationale for experimentation with a certain sample type no longer justifies keeping the sample). If a commercial product is developed from this research project, the sponsor owns the commercial product. The subject has no commercial rights to such product and has no commercial rights to the data, information, discoveries, or derivative materials gained or produced from the sample.

## **8. WITHDRAWAL FROM TREATMENT, PROCEDURES, AND STUDY**

### **8.1 Subjects' Decision to Withdraw**

Subjects have the right to withdraw from the study at any time and for any reason without prejudice to their future medical care by the physician or at the institution.

Subjects can decline to continue receiving investigational product and/or other protocol-required therapies or procedures at any time during the study but continue participation in the study. If this occurs, the investigator is to discuss with the subject the appropriate processes for discontinuation from investigational product, device or other protocol-required therapies and must discuss with the subject the options for continuation of the Schedule of Assessments ([Table 4](#) and [Table 5](#)) including different

options of follow-up (eg, in person, by phone/mail, through family/friends, in correspondence/communication with other treating physicians, from the review of medical records) and collection of data, including endpoints, and adverse events. Subjects who have discontinued investigational product and/or protocol required therapies or procedures should not be automatically removed from the study. Whenever safe and feasible it is imperative that subjects remain on-study to ensure safety surveillance and/or collection of outcome data. The investigator must document the level of follow-up that is agreed to by the subject.

Withdrawal of consent for a study means that the subject does not wish to receive further protocol-required therapies or procedures, and the subject does not wish to or is unable to continue further study participation. Subject data up to withdrawal of consent will be included in the analysis of the study, and where permitted, publically available data can be included after withdrawal of consent. The investigator is to discuss with the subject appropriate procedures for withdrawal from the study.

## **8.2 Investigator or Sponsor Decision to Withdraw or Terminate Subjects' Participation Prior to Study Completion**

The investigator and/or sponsor can decide to withdraw a subject(s) from investigational product, medical device(s), and/or other protocol required therapies, protocol procedures, or the study as a whole at any time prior to study completion.

Subjects may be eligible for continued treatment with Amgen investigational product(s) and/or other protocol required therapies by a separate protocol or as provided for by the local country's regulatory mechanism, based on parameters consistent with [Section 12.1](#).

## **8.3 Reasons for Removal From Treatment or Study**

### **8.3.1 Reasons for Removal From Treatment**

Reasons for removal from protocol-required investigational product(s) or procedural assessments include any of the following:

- subject request
- safety concern (eg, due to an adverse event, protocol deviation, non-compliance, pregnancy)
- death
- lost to follow-up
- decision by sponsor (other than subject request, safety concern, lost to follow-up)

### **8.3.2 Reasons for Removal From Study**

Reasons for removal of a subject from the study are:

- decision by sponsor
- withdrawal of consent from study
- death
- lost to follow-up

## **9. SAFETY DATA COLLECTION, RECORDING, AND REPORTING**

### **9.1 Definition of Safety Events**

#### **9.1.1 Adverse Events**

An adverse event is defined as any untoward medical occurrence in a clinical trial subject. The event does not necessarily have a causal relationship with study treatment. The investigator is responsible for ensuring that any adverse events observed by the investigator or reported by the subject are recorded in the subject's medical record.

The definition of adverse events includes worsening of a pre-existing medical condition. Worsening indicates that the pre-existing medical condition or underlying disease (eg, diabetes, migraine headaches, gout) has increased in severity, frequency, and/or duration more than would be expected and/or has an association with a significantly worse outcome than expected. A pre-existing condition that has not worsened more than anticipated (ie, more than usual fluctuation of disease) during the study, or involves an intervention such as elective cosmetic surgery or a medical procedure while on study, is not considered an adverse event.

The investigator's clinical judgment is used to determine whether a subject is to be removed from treatment due to an adverse event. In the event a subject requests to withdraw from protocol-required therapies or the study due to an adverse event, refer to [Section 8.1](#) for additional instructions on the procedures recommended for safe withdrawal from protocol-required therapies or the study.

#### **9.1.2 Serious Adverse Events**

A serious adverse event is defined as an adverse event that meets at least 1 of the following serious criteria:

- fatal
- life threatening (places the subject at immediate risk of death)
- requires in patient hospitalization or prolongation of existing hospitalization
- results in persistent or significant disability/incapacity

- congenital anomaly/birth defect
- other medically important serious event

An adverse event would meet the criterion of “requires hospitalization”, if the event necessitated an admission to a health care facility (eg, overnight stay).

If an investigator considers an event to be clinically important, but it does not meet any of the serious criteria, the event could be classified as a serious adverse event under the criterion of “other medically important serious event”. Examples of such events could include allergic bronchospasm, convulsions, blood dyscrasias, drug induced liver injury (DILI) (see [Appendix A](#) for DILI reporting criteria), or events that necessitate an emergency room visit, outpatient surgery, or urgent intervention.

## **9.2 Safety Event Reporting Procedures**

### **9.2.1 Adverse Events**

#### **9.2.1.1 Reporting Procedures for Adverse Events That do not Meet Serious Criteria**

The investigator is responsible for ensuring that all adverse events observed by the investigator or reported by the subject that occur after first dose of investigational product (AMG 529 or placebo) through the End of Study are reported using the Event CRF.

The investigator must assign the following adverse event attributes:

- Adverse event diagnosis or syndrome(s), if known (if not known, signs or symptoms),
- Dates of onset and resolution (if resolved),
- Severity (and/or toxicity per protocol),
- Assessment of relatedness to IP (AMG 529 or placebo)
- Assessment of relatedness to any study-mandated activity/procedure
- Action taken.

Determination of the severity of adverse events will be as follows: grade 1 = mild (eg, asymptomatic or mild symptoms, clinical or diagnostic observations only, intervention not indicated, or does not interfere with activity); grade 2 = moderate (eg, minimal intervention indicated or interferes with activity); grade 3 = severe (eg, medically significant but not immediately life-threatening, prevents daily activity, or requires treatment); grade 4 = life-threatening (ie, refers to an event in which the subject was, in the view of the investigator, at risk of death at the time of the event); and grade 5 = fatal.

The investigator must assess whether the adverse event is possibly related to the administration of investigational product (AMG 529 or placebo). This relationship is indicated by a “yes” or “no” response to the question: Is there a reasonable possibility that the event may have been caused by the investigational product (AMG 529 or placebo)? Relatedness means that there are facts or reasons to support a relationship between investigational product and the event.

The investigator must assess whether the adverse event is possibly related to any study mandated activity (eg, administration of investigational product and/or study procedure, including screening procedures). This relationship is indicated by a “yes” or “no” response to the question: Is there a reasonable possibility that the event may have been caused by a study activity (eg, administration of investigational product and/or study procedure)?

The investigator is responsible for reviewing laboratory test results and determining whether an abnormal value in an individual study subject represents a clinically significant change from the subject’s baseline values. In general, abnormal laboratory findings without clinical significance (based on the Investigator’s judgment) are not to be recorded as adverse events. However, laboratory value changes that require treatment or adjustment in current therapy are considered adverse events. Where applicable, clinical sequelae (not the laboratory abnormality) are to be recorded as the adverse event.

The investigator is expected to follow reported adverse events until stabilization or reversibility.

